2. V1 of this extension trial should be preferably performed during the EOS of the preceding BI 655130 parent trial. When the visits are performed on the same day duplicate procedures across studies are performed once during the EOS/V1. If these visits are not performed on the same day then all V1 procedures need to be performed at that visit. The only exception is Infection Testing which does not have to be repeated if performed at EOS of the parent trial and there is a <12 week gap from EOS of parent trial to V1 of this trial. Refer also to [Section 6.2.1](#)
3. After the individual patient's end of the trial the investigator should report only any cancers of new histology and exacerbations of existing cancer, study treatment related SAEs and study treatment related AESIs of which the investigator may become aware of and only via the BI SAE form. Refer to [Section 5.2.6.2.1](#).
4. All patients who receive at least one dose in the trial, including those who discontinue treatment prematurely, should complete the EOT visit as soon as possible and complete the EOS visit 16 weeks after the date of last trial drug administration.
5. Where possible, electrocardiogram (ECG) measurements should precede blood sampling and drug administration. Refer to [Section 5.2.4](#)
6. Body Surface Area (BSA) will be calculated from Part A of the SCORAD. All assessments must be done prior to trial drug administration. The questionnaires completed by patients should be done first before the investigator assessments. Refer to [Section 6.2](#)
7. Only applicable for women of childbearing potential. Urine pregnancy tests will be performed at all visits indicated in the [Flow Chart](#). Urine pregnancy testing should be done prior to administration of study drug. Study drug should only be administered in case of a negative test result. In case of a positive urine pregnancy test, a serum pregnancy test will be performed at the central laboratory.
8. Complete Physical Examination (PE) includes general appearance as well as evaluation of all organ systems.
9. Targeted physical examination includes evaluation of organ systems associated with AE(s) symptoms or laboratory abnormalities.
10. Vital signs will be assessed pre dose as well as within 1 hour post dose.
11. Safety laboratory tests include clinical chemistry, haematology, coagulation, and urinalysis, and will be performed centrally. Where possible, safety laboratory tests are to be drawn prior to dosing.

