5.2.2 Vital signs

Vital signs will be performed pre-dose as well as within 1 hour post dose (Refer to [Flow Chart](#)). Vital signs include systolic and diastolic blood pressure, pulse rate (electronically or by palpation count for 1 minute) and body temperature. Vital signs will be measured after the patients has been sitting comfortably (resting) for at least 5 minutes. The results must be included in the source documents available at the site.

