6.2.2 Treatment period

After Visit 1, the patient will return for 51 additional visits during the treatment period. The duration between visits is 4 weeks. At every visit study drug will be administered.

If the patient completes this 4 year study, the last study drug administration will be at Visit 52 (EOT).

Drug administration and rules for early/late visits

It's important for the patient to adhere to the visit schedule per the [Flow Chart](#). The visit schedule should always align with Visit 1.

The IRT system has been set up to make sure that a patient does not receive 2 doses of medication in less than a 14 day period.

In these scenarios, the patient should conduct the visit but skip the dose. The patient should be administered the dose at the next scheduled visit.

Pregnancy Testing

Urine pregnancy testing for all woman of childbearing potential will be conducted on-site prior to every dosing and must be negative to receive study drug. A positive urine test must be confirmed with a serum pregnancy test at the central laboratory.

See the [Flow Chart](#) for details of all procedures required at each visit.

Unscheduled visits

If a patient suspects that their AD is worsening in between the protocol specified scheduled visits, they should make an unscheduled visit and return to the clinic/site for assessment. The patient may be called in for additional unscheduled visits due to safety reason at the discretion of the investigator or the sponsor, unless the patient has withdrawn his/her consent. The patient may also contact the site due to safety reason for an unscheduled visit. The unscheduled visit may include additional collection of blood samples for safety reasons. The unscheduled visit may also include additional assessments deemed necessary by the investigator such as laboratory samples, ECGs, or other procedures which were missed at a previous visit. All unscheduled visits should be described (including the reason for the visit) and documented in the medical/source record, and in the eCRF.

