6.7 BASELINE, TIME WINDOWS AND CALCULATED VISITS

Measurements reported with date and time and taken prior to start of administration of trial treatment will be considered pre-treatment values. Measurements reported with a date only (and no time) and taken on the day of first administration of trial treatment will also be considered pre-treatment values. These pre-treatment values will be assigned to visits according to the nominal visit number as recorded on the eCRF or as provided by the laboratory. For definitions used in Safety analyses, refer to [Section 7.8](#).

There will be two different baseline definitions used in the analyses:

1. Baseline for this extension trial – defined as the last measurement recorded before the first trial medication administration in this study.

2. Baseline for the parent trial (1638-0032) – defined as the measurement recorded at randomisation visit (Visit 2) of the parent trial. If the data at Visit 2 is missing, then the data from Visit 1 of the parent trial will be considered baseline.

Two separate analyses will be conducted, using the baselines as defined above.

Measurements taken after start of administration of trial treatment will be considered either on- or off-treatment values based on the definition in [Section 6.1](#), and will be assigned to visits for statistical analysis, if applicable, as defined below.

Analysis of AE data, concomitant medication or non-drug therapies will not be based on visits. Therefore, no assignment to time windows will be necessary for such data.

For derivation of the last value on treatment, minimum value on treatment, and maximum value in the trial phase, all values from the relevant phase (whether or not collected in any time window; see [Table 6.1: 1](#) for definition of the trial phases) will be considered; these will be derived for analysis of laboratory and vital signs data. For identification of potentially clinically significant abnormal laboratory values, all values (whether or not selected in any time window) before the date of EoS Participation visit will be considered.

A graphical analysis of the ALT and total bilirubin will be performed (so called eDISH plot) based on the available data obtained during the on-treatment period.

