All other safety, efficacy and biomarker measurements will be assigned to visits based on extended time windows around the planned visit dates, defined relative to the day of first trial treatment (which is scheduled for Visit V2). These extended time windows are defined in [Table 6.7: 1](#).

Table 6.7: 1 Time windows for assignment of efficacy, safety lab, vital signs, and biomarker measurements to visits for statistical analysis

Visit number / name	Visit label	Planned day	Time window (Days)				
			Window (per CTP)	Start (per CTP)	End (per CTP)	Start (extended)	End (extended)
V1	Day 1	Day 1	n/a	1 ^A	1	1 ^A	1
V2	Week 4	Day 29	+/- 14	15	43	2	43
V3	Week 8	Day 57	+/- 14	44	71	44	71
V4	Week 12	Day 85	+/- 14	72	99	72	99
V5	Week 16	Day 113	+/- 14	100	127	100	127
V6	Week 20	Day 141	+/- 14	128	155	128	155
V7	Week 24	Day 169	+/- 14	156	183	156	183
V8	Week 28	Day 197	+/- 14	184	211	184	211
V9	Week 32	Day 225	+/- 14	212	239	212	239
V10	Week 36	Day 253	+/- 14	240	267	240	267
V11	Week 40	Day 281	+/- 14	268	295	268	295
V12	Week 44	Day 309	+/- 14	296	323	296	323
V13	Week 48	Day 337	+/- 14	324	351	324	351
V14	Week 52	Day 365	+/- 14	352	379	352	379
V15	Week 56	Day 393	+/- 14	380	407	380	407
V16	Week 60	Day 421	+/- 14	408	435	408	435
V17	Week 64	Day 449	+/- 14	436	463	436	463
V18	Week 68	Day 477	+/- 14	464	491	464	491
V19	Week 72	Day 505	+/- 14	492	519	492	519
V20	Week 76	Day 533	+/- 14	520	547	520	547
V21	Week 80	Day 561	+/- 14	548	575	548	575
V22	Week 84	Day 589	+/- 14	576	603	576	603
V23	Week 88	Day 617	+/- 14	604	631	604	631
V24	Week 92	Day 645	+/- 14	632	659	632	659
V25	Week 96	Day 673	+/- 14	660	687	660	687
V26	Week 100	Day 701	+/- 14	688	715	688	715
V27	Week 104	Day 729	+/- 14	716	743	716	743
...
V52	EoT	Day 1429	+/- 14	1415	1443	1415	1443
V53	EoS	Day 1541	+/- 14	1528	1555	1444	1555/EoT+ 16weeks

Days are counted relative to the day of first treatment, which is defined as Day 1.

^A Note that measurements made at Day 1 and assigned to the on-treatment period (because mistakenly made after start of injection of trial treatment) via assessment on date and time (i.e. safety laboratory) will not be assigned to Day 1. Such data will be listed only.

Repeated and unscheduled efficacy, safety and biomarker measurements will be handled similarly to scheduled measurements and will also be assigned to a time window depending upon the date of measurement.

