Only one observation per time window will be selected for statistical analysis at a particular visit – the value which is closest to the protocol planned visit day will be selected. If there are two observations which have the same difference in days to the planned day, the later value will be selected. If there are two observations on the same day, the worst value will be selected.

Assignment of efficacy observations to visits based on time windows will be based on the non-imputed (observed) data.

For visits without an assigned value based on time windows, a value will thereafter be imputed as defined in [Section 6.6](#). Imputation of efficacy endpoints, when applicable, will be performed based on all available observations obtained during the on-treatment period, irrespective of whether the observation was selected in any time window.

In addition, separate analyses will be performed using the parent trial baseline. Baseline value will then be defined the same way as in the parent trial (1368-0032) and will be taken from that parent trial.

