7.8.3 Vital signs

The analyses of vital signs (blood pressure, pulse rate, body temperature and body weight) will be descriptive in nature.

Descriptive statistics of vital signs over time and for the difference from baseline (see [Section 6.7](#)) will be provided by treatment, including summaries of the last value during the on-treatment period, the minimum value during on-treatment period, and the maximum value during on-treatment period (see [Table 6.1: 1](#) for definition of the on-treatment period).

Clinically relevant findings in vital signs data will be reported as baseline conditions (at screening) or as AEs (during the trial) if judged clinically relevant by the investigator, and will be analysed as such.

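### At dosing visits after Day 1, the same-day worst-value rule sets the worse of two vital-sign readings against a single-reading baseline, which shifts the by-visit change in an undefined direction

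*SAP*

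**What the plan says.** **Two readings per dosing visit.** Protocol Flow Chart footnote 10: "Vital signs will be assessed pre dose as well as within 1 hour post dose". Protocol 5.2.2 repeats it: "Vital signs will be performed pre-dose as well as within 1 hour post dose". Protocol 6.2.2 says of the treatment period: "At every visit study drug will be administered". It counts 51 visits after Visit 1, the last being Visit 52.

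**One value per visit.** The title of SAP Table 6.7:1 includes vital signs: "Time windows for assignment of efficacy, safety lab, vital signs, and biomarker measurements to visits for statistical analysis". The text after the table adds "Only one observation per time window will be selected for statistical analysis at a particular visit". The value nearest the planned day is taken. If two values are equally near, the later one is taken. For a same-day pair: "If there are two observations on the same day, the worst value will be selected".

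**Baseline.** SAP 6.7 defines the extension baseline as the last measurement before the first dose in this trial. Footnote A to Table 6.7:1 says that Day 1 measurements identified by date and time as post-injection are listed only; its example is safety laboratory. Measurements with a date but no time are treated differently. Those "taken on the day of first administration of trial treatment will also be considered pre-treatment values".

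**Output.** SAP 7.8.3 plans "Descriptive statistics of vital signs over time and for the difference from baseline", plus last, minimum and maximum on-treatment values. It has no selection rule of its own, no pre-dose and post-dose display, and no definition of *worst*. For laboratory data, by contrast, SAP 7.8.2 refers repeat values at a visit to a sponsor guidance.

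**The concern.** A same-day rule of this kind suits an occasional repeat measurement. Here the same-day pair is the planned norm for blood pressure, pulse and temperature at each dosing visit, so the rule decides almost every tabulated value after Day 1. The more extreme of two readings is, on average, further out than a single reading. Subtracting a single-reading baseline leaves a difference that has nothing to do with treatment.

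Three things make this worth correcting. Protocol 7.2.5 promises to assess vital signs for change against findings before treatment, which is the comparison affected. The trial has one arm, so no control group carries the same artefact and cancels it. And the post-dose reading serves to show acute effects of an injection; the rule mixes those with long-term change, so the table shows neither cleanly.

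**Working it through.** The documents give no vital-sign figure to reproduce and no SD or correlation for vital signs. The structure below comes from the documents; the SDs and correlations are assumptions.

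**1. Which visits are affected.** Those with a dose after Day 1: at most Visits 2 to 52, so 51 visits. The following have no planned pre/post pair:
- the end-of-study visit;
- the end-of-treatment visit after early discontinuation, where no dose is given (Flow Chart footnote 15);
- visits where the dose is skipped (Protocol 6.2.2);
- body weight.

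**2. Size with no drug effect.** Let the pre-dose and post-dose readings be normal with the same mean and independent within-visit errors of SD w. Then

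E[higher of two] − mean = w/√π = 0.564 × w,

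and the lower of two gives the same amount with a minus sign. A single-reading baseline has expectation equal to the mean, so the expected change is +0.564w or −0.564w. For systolic pressure:

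| Assumed w (mmHg) | Expected change (mmHg) |
|---|---|
| 4 | ±2.3 |
| 6 | ±3.4 |
| 8 | ±4.5 |

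**3. The same result from total SD and correlation.** If s is the SD across patients and ρ the correlation of two readings, then w = s√(1−ρ) and the shift is s√((1−ρ)/π). With ρ from 0.5 to 0.9:

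| Measure | Assumed s | Shift (±) |
|---|---|---|
| Systolic pressure | 10 to 20 mmHg | 1.8 to 8.0 mmHg |
| Pulse | 8 to 12 bpm | 1.4 to 4.8 bpm |
| Temperature | 0.3 to 0.4 °C | 0.05 to 0.16 °C |

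For example, s = 15 and ρ = 0.8 give 15 × √(0.2/3.1416) = 3.8 mmHg.

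**4. Simulation check.** 40 patients, s = 15 mmHg, ρ = 0.8 (also between baseline and visit readings), no drug effect, 20,000 replicates:

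| Visit value | Baseline | Mean change (mmHg) |
|---|---|---|
| Highest of two | Single | +3.8 |
| Lowest of two | Single | −3.8 |
| Pre-dose only | Single | 0.0 |
| Mean of two | Single | 0.0 |
| Highest of two | Highest of two | 0.0 |

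The standard error of the mean change in the first row is 1.37, so the shift is 3.8/1.37 = 2.8 standard errors. The share of patients above their own baseline rises from 50% to 67%.

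**5. The date-only branch.** Steps 2 to 4 need a single pre-dose baseline, so Day 1 times must be recorded. If vital signs carry a date only, both Day 1 readings count as pre-treatment. Baseline could then be the pre-dose reading, the post-dose reading or, if the same-day rule were applied to it, the worse of the two. Only the last removes the shift (final row of the table).

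**The case against.** **The plan may handle this elsewhere.** SAP 7.8 says safety analyses follow sponsor standards that are not supplied, and parts of SAP 5.4 are not visible. Either might separate the two time points. But SAP 6.7 states an explicit rule, its table names vital signs, and nothing visible exempts them. SAP 7.8.3 says over time where 7.8.2 says by visit for laboratory data, but Table 6.7:1 is where vital signs are assigned to visits for analysis.

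**The tie rule could apply instead.** Two same-day readings are equally far from the planned day, so the later-value rule also fits literally. The same-day rule is the more specific one. Taking the later value would still set post-dose readings against a pre-dose baseline.

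**The consequence is limited.** This stands. Last, minimum and maximum on-treatment values draw on all readings and bypass the selection. Individual values are listed. Clinically relevant findings are reported as adverse events, and adverse-event analysis is not visit-based. No secondary endpoint uses vital signs, and nothing is tested.

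**Stronger readings to avoid.** A reader might infer a spurious rise at every visit. The documents do not support that: visits without a dose are outside the mechanism, and *worst* is undefined. It could mean highest, lowest or furthest from normal; in the last case the direction may differ by patient and the formula does not apply. A reader might also infer that Day 1 post-dose readings contaminate baseline. Under footnote A, timed post-dose readings are listed only, so that problem arises only if times are missing.

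**Conclusion.** The concern holds within limits. At dosing visits after Day 1, with measurement times recorded, following SAP 6.7 as written biases the by-visit change in blood pressure, pulse and temperature when the drug has no effect. If *worst* means highest or lowest, the bias is about 0.56 times the within-visit SD, illustratively ±2.3 to ±4.5 mmHg systolic. That size assumes normal readings with equal means, independent within-visit errors and an SD of 4 to 8 mmHg that the documents do not supply. The mechanism does not depend on those figures; the sign depends on a definition the SAP does not give. If times are not recorded, the defect becomes an ambiguous baseline, and the shift may or may not remain.

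The calculation concerns the extension baseline. I have not extended it to the parent-trial baseline, because the parent trial's vital-sign schedule is not in the documents.

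The damage is to descriptive vital-sign tables only. It is worth correcting because those tables are part of the long-term safety account and there is no control arm to expose the artefact.

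**What to change.** In SAP 6.7, exempt vital signs from the same-day worst-value rule and state that the pre-dose reading is used for the extension baseline and for all by-visit values and changes. Classify Day 1 vital signs by planned time point (pre-dose or post-dose), not by date alone, so that baseline is determined whether or not a clock time was recorded.

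Optionally, tabulate post-dose minus pre-dose change separately, so that acute effects are visible. This is an added display and is not needed to remove the bias.

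The cost is a few SAP sentences and modest programming. The schedule already provides both readings, so no new data are needed. Without the optional display, post-dose readings would appear only in the listings and in the last, minimum and maximum on-treatment summaries.

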7. PLANNED ANALYSIS

All efficacy and safety analyses will be purely exploratory in nature. The following analyses are planned throughout the trial.

- **Status review (at the requested timelines)**

The status reviews will be performed periodically and on demand. The analyses will include all data available at the time of the snapshot. The analyses are planned to be defined for each time point as requests in the CSAP, depending on the requirements.

- **Final analysis (Week 220)**

The analysis of the entire efficacy, safety, PK, and biomarker data collected through the full 220 weeks of follow-up will be performed once all entered patients have completed the trial (up to EoS Visit); at that time point, a final database lock will be done and all data through week 220 will be reported. The majority of biomarkers will be reported outside the CTR.

General Remarks

The format of the listings and tables will follow the BI guideline “Standards for Reporting of Clinical Trials and Project Summaries” [BI-KMED-BDS-HTG-0045] (7) with the exception of those generated for PK.

The individual values of all patients will be listed, including those collected during the off-treatment period. Listings will generally be sorted by country, centre number, patient number and visit (if visit is applicable in the respective listing). AE listings will be sorted by treatment (see [Section 7.8.1](#) below for details).

The following standard descriptive statistical parameters will be displayed in summary tables of continuous variables:

N	number of non-missing observations
Mean	arithmetic mean
SD	standard deviation
Min	minimum
Q1	lower quartile
Median	median
Q3	upper quartile
Max	maximum

The data format for descriptive statistics of concentrations will be identical with the data format of the respective concentrations.

Statistical parameters will be displayed to a defined number of decimal places as specified in the BI guideline “Standards for Reporting of Clinical Trials and Project Summaries” (7).

Tabulations of frequencies for categorical data will include all possible categories and will display the number of observations in a category as well as the percentage (%) relative to the respective treatment. Percentages will be rounded to one decimal place. The category missing will be displayed if and only if there actually are missing values. Percentages will be based on all patients in the respective patient set whether they have non-missing values or not.

Disposition of the patient population participating in the trial (overall) will be summarised by presentation of the frequency of patients entered, treated, entered but not treated, who completed all doses of trial medication as planned (until the trial termination), who prematurely discontinued study drug administration by reason, who completed the observational period as planned, who prematurely discontinued study participation. Disposition will be listed by country.

The frequency of patients with iPDs will be presented for the SAF, overall. The iPDs will be listed per patient indicating whether or not the iPD led to exclusion from patient sets analysed.

The frequency of patients in each of the different analysis sets will also be overall.

7.1 DEMOGRAPHIC AND OTHER BASELINE CHARACTERISTICS

Only descriptive statistics are planned for this section of the CTR.

Descriptive statistics will be presented overall for demographic parameters and baseline characteristics, based on the SAF.

For the continuous variables described below, categories are defined in [Table 7.1: 1](#). These variables will be presented according to the number and percentage of patients in each category.

Table 7.1: 1 Categories for summary of continuous variables

Variable	Categories
Age	< 30 years
	≥ 30 years
	< 65 years
	≥ 65 years
BMI	< 25 kg/m ²
	25 to < 30 kg/m ²
	≥ 30 kg/m ²
Time since first diagnosis	≤ 1 year
	> 1 to ≤ 5 years
	> 5 to ≤ 10 years
	> 10 years
Age at disease onset	≤ 12 years old
	> 12 years old

